# 2. AIMS AND OBJECTIVES

## 2.1. Main study

- To evaluate the accuracy and precision of candidate biomarkers (imaging, clinical, biofluid) in predicting prognosis in mTBI due to impact, blast and sport concussion.
- To identify biomarkers at the time of injury to enable a rapid decision to return to play, work or duty.
- To develop a multifaceted biomarker algorithm to predict prognosis in mTBI.

Biomarkers to be assessed are summarised in Table 2 below, and will include brain imaging (structural, functional, MRI, MEG, EEG), biofluid and hormone biomarkers, visual and vestibular disturbances, cerebral physiology, physical function, mental health, headache markers and cognitive dysfunction.

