## 3.6. Recruitment

Participants will be recruited from the study centres and their dependant patient identification centres (PICs).

Recruitment of mTBI patients will be from dedicated concussion/mTBI clinics and emergency departments.

- Birmingham University Hospitals Birmingham, Concussion service, Trauma service
- Military Defence Medical Rehabilitation Centre, mTBI team, rehab teams
- University Hospitals Coventry and Warwickshire
- Further centres

Healthy controls will be recruited from study centres, local sports clubs, etc. and online and poster advertisements (see Section 6.1).

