## 5.4. Study entry points

## 5.4.1. mTBI patients

mTBI patients may enter the study at any time up until 3 months after their injury, and will have their first assessment at the next timepoint after their injury:

- Within 7 days of the injury. After consenting, visit 1 procedures should be completed (section 7.5).
- 21 days (± 7 days) post-injury. After consenting, visit 3 should be booked.
- 3 months (± 7 days) post-injury After consenting, visit 8 should be booked.

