# **7. STUDY ASSESSMENTS**

## 7.1. mTBI patients

**mTBI patients** enter the study within 7 days of injury,  $\leq$ day 21, or  $\leq$ 3 months, at either visit 1, visit 2 or visit 7 respectively. Patients will be approached consecutively until a total of 610 is reached.

mTBI patients enrolled within 7 days of injury will enter the study at visit 1, with subsequent followup at day 21 (±7 days) for visits 2, 3, 4, 5; at 2 months ±7 days (visit 6); and at 3 months ±7 days (visits 7, 8, 9, 10).

All mTBI patients will be followed up at 6 months (visits 11 and 12); at 12 months (visit 13); and at 24 months (visit 14) (all ±14 days).

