#### mTBI-Predict protocol

Daily headache /sleep diary, Actigraphy		Cont	inuous from er	ntry to month a	3 visit		
Exploratory imaging			x				х

\*Entry points are visits 1, 2, or 7.

Assessments in green are exploratory and will be discontinued after 50 mTBI patients and 50 healthy controls have completed them.

Assessments marked (x) will be done if not already carried out.

Visit	11	12	13	14
Time-point from injury	6 months (assessment v	window: ± 14 days)	12 months (± 14 days)	24 months (± 14 days)
Location	Remote	Research Facility	Remote	Remote
Confirm consent to continue	x	x	x	x
Clinical assessment day		x		
Remote assessments	х		х	Х
Daily headache /sleep diary, Actigraphy	Continuous for 1 month prior to visit		Continuous for 1 month prior to visit	Continuous for 1 month prior to visit
Cognition mini-battery	Weekly for 1 month prior to visit		Weekly for 1 month prior to visit	Weekly for 1 month prior to visit

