### 14.4. Development of a prognostic model

We aim to develop multivariable statistical models that can predict sequelae of mTBI using the investigated biomarkers. The sequelae of mTBI being examined are headache, vestibular dysfunction, mental health (depression, PTSD), cognition, global function and full return to work, play or duty. These clinical outcomes are measured via mean monthly headache days, vestibular disturbance questionnaire, self-reported PHQ-9, self-reported PCL-5, corrected global composite score, and MPAI, respectively. Global composite score and MPAI are continuous outcomes; monthly headache days is a count outcome; and clinical thresholds to PHQ-9 and PCL5 will categorise patients into those with and without depression and PTSD respectively (binary outcomes). Each of these outcomes will be measured at 6-, 12- and 24-months post-injury.

Whilst absolute values of biomarkers will be valuable all biomarkers are measured on multiple occasions, as such characteristics such as the rate of change of biomarkers and time until normalisation will also be considered as potentially important data in their own right.

We aim to recruit 610 participants to follow-up for the prognostic modelling phase of the project. At 6 months, for each of the headache, depression and PTSD outcomes, we will have sufficient sample size to investigate a model with 10 candidate parameters; for the global composite score and MPAI outcomes, we will have sufficient sample size to investigate a model with 44 parameters. Sample size calculations were based on methods proposed by Riley [222, 223]. This will allow for 10% drop out which will be reviewed, and the analysis plan modified accordingly.

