Depending on the type of outcome, various types of statistical modelling approaches will be used. For example, continuous, binary and count outcomes will be modelled using linear, logistic and Poisson regressions respectively. We will build multivariable models that can predict clinical outcomes primarily at 6 months (secondarily, we may investigate outcomes at 12 and 24 months), based on 21-day biomarker data. We will also examine how changes to these biomarkers from 21 days to three months affect the clinical outcome. Models will be developed in line with best practice, using multiple imputation, backwards selection, and multivariable fractional polynomials in the development, as appropriate. We will internally validate the models produced using bootstrapping techniques and allow for optimism by applying a uniform shrinkage factor. Any multivariable models produced will be checked for compliance to model assumptions. Model performance will be assessed in terms of prediction and calibration, for example C-index for the logistic models.

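### The 610 and its 10- and 44-parameter limits count 3-month entrants who have no 21-day biomarkers, and section 14.4 names no model for the time-of-injury objective

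*Protocol*

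**What the plan says.** **Predictor time.** Section 14.4 sets outcomes mainly at 6 months and adds: "secondarily, we may investigate outcomes at 12 and 24 months), based on 21-day biomarker data". The one further time-specific analysis there also needs a 21-day value: "We will also examine how changes to these biomarkers from 21 days to three months affect the clinical outcome".

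**Who is counted.** Section 14.4: "We aim to recruit 610 participants to follow-up for the prognostic modelling phase of the project". Section 7.1: "Patients will be approached consecutively until a total of 610 is reached". No expected share or cap by entry route is given.

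**Entry.** Section 5.4.1: "mTBI patients may enter the study at any time up until 3 months after their injury". A patient's first assessment is at the next scheduled time point. The footnote to Table 4 in section 7.4 confirms: "Entry points are visits 1, 2, or 7". Visit 7 is the 3-month remote assessment. The 21-day window is plus or minus 7 days, so a patient enrolled after day 28 starts at 3 months. Section 7.8 makes specific provision for such entrants, and no make-up of the 21-day visits is described.

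**Size.** Section 14.4 states 10 candidate parameters for headache, depression and PTSD, and 44 for the cognitive composite score and MPAI, after a 10% dropout allowance.

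**Objective.** Section 2.1: "To identify biomarkers at the time of injury to enable a rapid decision to return to play, work or duty". Visit 1, within 7 days of injury, collects blood, saliva and tears (section 7.5.1).

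**The concern.** A participant contributes directly to a 21-day model only if 21-day biomarkers were measured. The protocol counts everyone who enters, then deducts only for dropout. Dropout means losing people who were assessed. A 3-month entrant may complete every later visit and still lack the whole 21-day panel. The parameter limits therefore describe a data set larger than the one the model will have, by an amount the protocol neither estimates nor controls. With a limit of only 10 parameters for three of the outcomes, losing one to four of them affects which biomarkers can be considered. Keeping 10 and 44 regardless would mean more overfitting than the calculation was meant to allow.

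Separately, a model whose predictors are measured at about day 21 cannot inform a rapid decision at the time of injury. As section 14.4 stands, that objective has samples but no named analysis.

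**Working it through.** **Inputs from the protocol (section 14.4):** 610 recruits; 10% dropout; 10 and 44 parameters; published minimum-sample-size methods for prediction models. The target shrinkage S and the R² values are not stated.

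**Step 1. Net number.** 610 × 0.90 = 549.

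**Step 2. Reproduce the stated limits.** The shrinkage criterion is n = p / [(S − 1) ln(1 − R²/S)], so p = n × (S − 1) × ln(1 − R²/S). Inferred inputs: S = 0.90, R² = 0.15 for the 10-parameter outcomes and 0.50 for the 44-parameter outcomes.

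- 549 × 0.1 × [−ln(1 − 0.15/0.90)] = 10.01, so 10. In reverse, p = 10 needs n = 549, and 549/0.90 = 610 exactly.
- 549 × 0.1 × [−ln(1 − 0.50/0.90)] = 44.52, so 44. In reverse, p = 44 needs 543 and p = 45 needs 555.
- Cross-check with the linear-model form of the criterion at n = 549: S = 0.9015 at p = 44 and 0.8994 at p = 45, again 44.

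Both stated limits are recovered. Slack is nil for the first and 6 participants (549 − 543) for the second.

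**Step 3. Remove participants without 21-day data.** Let f be the share of the 610 entering at 3 months. It is an assumption. Take the same dropout on every route and no contribution from these entrants to the 21-day model. Then n = 549 × (1 − f). The last column is 549 / [0.90 × (1 − f)], rounded up.

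| f (assumed) | n with 21-day data | Limit stated as 10 | Limit stated as 44 | Recruits needed to keep 549 |
|---|---|---|---|---|
| 0% | 549 | 10 (10.01) | 44 (44.52) | 610 |
| 10% | 494 | 9 (9.01) | 40 (40.07) | 678 |
| 20% | 439 | 8 (8.01) | 35 (35.62) | 763 |
| 40% | 329 | 6 (6.01) | 26 (26.71) | 1017 |

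For fixed S and R² the limit is proportional to n, so the proportional loss under this criterion does not depend on the inferred values.

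**Step 4. Keep 10 and 44 anyway.** Solving the same formula for S gives expected shrinkage of about 0.88 for both models at f = 20%, and about 0.84 (10 parameters) and 0.85 (44 parameters) at f = 40%, against the inferred target of 0.90.

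**Step 5. Time-of-injury objective.** Set section 2.1 beside section 14.4. The objective concerns biomarkers at injury. The models named use day 21, and the change analysis runs from day 21 to 3 months. Visit-1 values are not named as predictors in any model.

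**The case against.** **Imputation.** Section 14.4 names multiple imputation where appropriate, and 3-month entrants supply nearly the same panel at 3 months (section 7.8 drops only hair) plus outcomes. A reader might infer that imputation is impossible here. It is not. It is weak: the entire 21-day block is absent together, would be filled from later values and outcomes, and requires late and early entrants to be comparable given what was observed. The protocol does not say imputation is meant for this. Zero contribution in the table is therefore a worst case for each f.

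**Unknown share.** This stands; f could be small. A reader might assume entry spread evenly over the 3 months, putting most patients after day 28. Emergency-department recruitment, consecutive approach (sections 3.6 and 7.1) and the aim of including new injuries (section 1.2.2) do not support that.

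**Who enters late.** One might infer that late entrants are clinic referrals with worse outcomes. Section 3.6 says only "Recruitment of mTBI patients will be from dedicated concussion/mTBI clinics and emergency departments" and does not link source to entry time, so a shift in outcome prevalence is conjecture.

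**Other models.** It would be too strong to say every planned model is fixed at day 21. The exploratory network modelling (section 1.11.2) refers to initial and longitudinal recordings, and section 14.4 will also consider rate of change and time to normalisation. None of these names a visit-1 model, and MEG and MRI start only at visit 4.

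**Left to the SAP.** Analysis sets and extra models often belong there, and day 21 is a defensible landmark because the full panel first exists then. But the protocol itself states the predictor time, the 610 and the limits, and these do not fit together.

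**Conclusion.** The point holds for the section 14.4 models. The 610 and the 10 and 44 limits make no allowance for 3-month entrants, and the stated capacity has almost no slack to absorb them. Each 10% of recruits entering at 3 months costs about one of the 10 parameters and four to five of the 44, if those entrants contribute nothing.

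Three qualifications apply. The share is unknown, so the losses are scenarios. S and R² are inferred, although they reproduce 549, 610, 10 and 44 together. The formula used for the 10-parameter limit is the binary one, while headache days are a count outcome under Poisson regression. The affected limits are for headache, depression, PTSD, the composite score and MPAI; section 14.4 gives none for the primary outcome of return to play, work or duty, so no figure here applies to it.

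It also holds that section 14.4 names no model for the time-of-injury objective. A reader might suppose the cognitive mini-battery is available by day 7. Section 7.5.1 places it, and the Rivermead questionnaire, between visits 1 and 2, which can run past day 7. Section 7.4 does list symptom questionnaires at visit 1, so which scores exist by day 7 must be settled.

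**What to change.** In section 14.4:

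1. Define the analysis set of the 21-day model as participants with a 21-day assessment. Restate the parameter limits on the projected size of that set, with S, R² and the assumed share of 3-month entrants written down. Monitor the number during recruitment, while the entry mix can still be watched.
2. Add a 3-month landmark model for all entrants with 3-month data, rather than relying on imputing the whole 21-day panel for those who entered at 3 months.
3. For the time-of-injury objective, name a model in patients entering within 7 days, using visit-1 blood, saliva and tears and any symptom scores actually collected by day 7. Give it its own parameter limit, set by the number of such entrants.

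This needs wording and some extra analysis of data already being collected. The price is a smaller stated n and lower limits for the 21-day model, and possibly a low limit for the early model.

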### 14.5. Relationships with collaborating consortia

We will seek to undertake exploratory analysis of the data with related international consortia where possible or appropriate. Furthermore, we will seek to cross-validate candidate biomarkers within the related mTBI populations of collaborating consortia.

# **15. STUDY ORGANISATIONAL STRUCTURE**

### 15.1. Sponsor

The Sponsor for this study is University of Birmingham (UoB).

#### **15.2.** Coordinating centre

The study coordinating centre (Study Office) is Birmingham Clinical Trials Unit (BCTU), based at UoB.

### **15.3.** Study Management Group (SMG)

The core SMG comprises individuals responsible for the day-to-day management of the study: the CI, lead statistician, trial team leader, study manager, programme manager, and lead clinical researchers. The role of the group is to monitor all aspects of the conduct and progress of the study, ensure that the protocol is adhered to and take appropriate action to safeguard participants and the quality of the study itself. The SMG will meet sufficiently frequently to fulfil its function.

An extended SMG including Workstream leads and other relevant co-investigators will meet as required to review progress, troubleshoot and plan strategically.

## **15.4.** Study Steering Committee (SSC)

A SSC, comprising independent and non-independent members, will be established for the mTBI-Predict study and will meet as required depending on the needs of the study. Membership and duties/responsibilities are outlined in the SSC Charter. In summary, the role of the SSC is to provide oversight of the study. The SSC will monitor study progress and conduct and provide advice on scientific credibility. The SSC will operate in accordance with a study specific SSC Charter.

### **15.5.** Data Monitoring Committee (DMC)

As there is no intervention in mTBI-Predict, it is considered that a DMC is not required.

## **15.6.** Chief Data Officer

A Chief Data Officer will work with each workstream and BCTU to ensure the quality of the data for the entire programme. The Chief Data Officer responsibilities will include:

- Developing an overarching strategy including design and description of standards for the data architecture within the programme.
- Provision of a coordinated view to harmonise the data from each workstream, whilst ensuring data integrity.
- Ensure all data are optimised to support the research objectives for patient benefit.

#### **15.7.** App oversight committee

The app oversight committee will oversee the configuration of the web and mobile App that will be used to collect cognitive, participant reported, and actigraphy data during the project. Work spans from definition of functionality and scheduling to oversight of development work as undertaken by H2 Cognitive Designs, and piloting of the App once it is available.

#### **15.8. Statistical oversight committee**

The statistical oversight committee will oversee the overall study analysis, readiness for analysis of the various data streams, and coordinate analyses involving cross-worksteam input.

### 15.9. Data oversight committee

The data oversight committee will work with the Chief Data Officer to establish and refine data policy, providing strategic direction for the project's data governance, including upload/download protocols, structure and information content. The committee will liaise with workstreams leads to ensure understanding of needs and requirements to allow collaborative research and standardisation of data collection to enable consistent and accurate data. The committee will review data at milestones to ensure consistency and inform adjustments to data policy.

### 15.10. Clinical facilitation committee

The clinical facilitation committee will work to monitor and refine recruitment and clinical study assessments, reporting to the study management group on conduct and progress.

#### **15.11. Finance**

The research costs of the study are funded by the UK Ministry of Defence and US Department of Defense awarded to [name], University of Birmingham. Additional costs such as service support costs associated with the study, e.g. gaining consent, are estimated in the Schedule of Events Cost Attribution Template. These costs should be met by accessing the Trust's Support for Science budget via the Local Comprehensive Research Network.

# **16. ETHICAL CONSIDERATIONS**

The study will be conducted in accordance with the UK Policy Framework for Health and Social Care Research and applicable UK Acts of Parliament and Statutory Instruments (and relevant subsequent amendments), which include Data Protection Act 2018 and Human Tissue Act 2004 and the Principles of GCP as set out in the UK Statutory Instrument (2004/1031; and subsequent amendments). The protocol will be submitted to and approved by the REC prior to the study's start.

Before any participants are enrolled into the study, the PI at each site is required to obtain the necessary local approval.

It is the responsibility of the PI to ensure that all subsequent amendments gain the necessary local approval. This does not affect the individual clinicians' responsibility to take immediate action if thought necessary to protect the health and interest of individual participants.

# **17. DATA PROTECTION AND CONFIDENTIALITY**

Personal data and sensitive personal data recorded electronically and on all documents will be regarded as strictly confidential and will be handled and stored in accordance with the Data Protection Act 2018 (and subsequent amendments).

Participants will only be identified by their unique study identification number and initials on CRFs and on any correspondence with the Study Office.

For all participants, full name, full date of birth, sex at birth, and NHS number will be collected on the Registration eCRF. The participant's full name will also be collected on the participant consent forms in addition to their email address and/or mobile number.

Other personal data categories that will be collected and analysed include health information and medical history.

Participants will acknowledge the electronic transfer and storage of their ICF to the Study Office. This will be used to perform central monitoring of the consent process. Participants will acknowledge the transfer of their personal data for the purpose of processing for medical research to collaborating institutions. Participants will acknowledge the transfer of their personal data to H2 Cognitive Designs who will be processing data collected by the app on behalf of the study.

In the case of specific issues and/or queries from the regulatory authorities, it will be necessary to have access to the complete study records. Representatives of the mTBI-Predict study team and sponsor may be required to have access to participants' notes for quality assurance purposes, but participants should be reassured that their confidentiality will be respected at all times. The Study Office will maintain the confidentiality of all participant data and will not disclose information by which participants may be identified to any third party.

## **18. FINANCIAL AND OTHER COMPETING INTERESTS**

There are no financial or other competing interests related to the results of this study. Members of the SSC are required to provide declarations on potential competing interests as part of their membership of the committees. Authors are similarly required to provide declarations at the time of submission to publishers.

### **19. INSURANCE AND INDEMNITY**

UoB has in place Clinical Trials indemnity coverage for this study which provides cover to UoB for harm which comes about through the University's, or its staff's, negligence in relation to the design or management of the study and may alternatively, and at UoB's discretion, provide cover for nonnegligent harm to participants.

With respect to the conduct of the study at Site and other clinical care of the patient, responsibility for the care of the patients remains with the NHS organisation responsible for the Clinical Site and is therefore indemnified through the NHS Litigation Authority.

# 20. POST-STUDY CARE

Participants will continue to receive standard care during and after participation in mTBI-Predict.

# 21. ACCESS TO FINAL DATASET

The final dataset will be available to members of the Study Management and co-applicant group who need access to the data to undertake the final analyses.

Requests for data generated during this study will be considered by BCTU. Data will typically be available six months after the primary publication unless it is not possible to share the data (for example: the study results are to be used as part of a regulatory submission, the release of the data is subject to the approval of a third party who withholds their consent, or BCTU is not the controller of the data).

Only scientifically sound proposals from appropriately qualified Research Groups will be considered for data sharing. The request will be reviewed by the BCTU Data Sharing Committee in discussion with the CI and, where appropriate (or in the absence of the CI) any of the following: the Sponsor, the SMG, and the SSC.

A formal Data Sharing Agreement may be required between respective organisations once release of the data is approved and before data can be released. Data will be fully de-identified (anonymised) unless the agreement covers transfer of participant identifiable information. Any data transfer will use a secure and encrypted method.

